Am I Stoned? Developing a field sobriety test for cannabis use.

PI: [name]

Other investigators: [name], [name], [name]

Jan 11, 2017

The rapid increase in use of cannabis across the US has raised public health concerns about safety related to the drug, especially risks related to impairments in cognitive performance and judgment. There is evidence from controlled studies that marijuana and its active ingredient delta-9-tetrahydrocannabinol (THC) can impair memory, reaction time and attention. However, it is not clear to what extent these impairments are manifested in naturalistic, non-laboratory settings, and importantly, it is not clear to what extent users are aware of their impairments after drug use. A lack of awareness of impaired performance would pose an especially great risk to public safety compared to deficits that are clearly apparent to the user.

We have developed a prototype for an app called Am I Stoned? that could be used by marijuana users in the non-laboratory setting to assess their level of impairment relative to their non-intoxicated state. Information about impairments and awareness of impairment would be of value to researchers studying the safety of the drug, as well as to users who are concerned about their ability to function safely. In the ultimate version of this app, users would engage in a baseline determination phase and then a drug utilization phase. The baseline determination phase would require them to complete simple tasks on a hand-held device (e.g., phone) on 6 occasions when they have not used any drugs, and on 6 occasions when they have used, provide personalized data about their performance with and without the drug. Then in the drug utilization phase, users would use the app to estimate their own level of impairment with a quick phone-based assessment. Importantly, users would also be asked to estimate their level of performance to obtain an indicator of how aware they are of their intoxicated state. The data would be stored in a coded form for use by researchers and by users themselves.

A critical first step in developing this app is to conduct a controlled, laboratory-based study with known doses of THC to determine the sensitivity and time course of the impairments in app-based task performance. Therefore our Specific Aims for this administrative supplement are as follows:

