An important feature of our to-be-developed app *Am I Stoned?* is that it will provide feedback on users' perceptions of impairment, relative to their actual impairment. Drug users are not always able to judge their own level of performance under the influence of a drug (Goldstein et al, 2009). Importantly, this lack of knowledge greatly heightens the risk for engaging in unsafe behaviors. Indeed, drugs themselves may have direct effects on cognitive judgment, which may impair the users' ability to detect degradation in their performance. Evidence from controlled studies indicates that drug users often underestimate the extent to which drugs impair their performance. For example Brumbeck et al (2007) reported dissociations between perceived and actual impairment after an acute dose of alcohol among light and heavy drinkers. Both light and heavy drinkers were equally impaired by objective tests, but the heavy drinkers underestimated their level of impairment, compared to the light drinkers. It is not known whether marijuana users are able to estimate their own level of impairment. A lack of awareness between perceived and actual performance impairment has important consequences for safety of drug use.

This project will also address a related question: Are the user's feelings of intoxication related to his or her impaired performance? In general, feelings of intoxication are related to performance impairments and both are related to the dose of drug. However, tolerance can develop to either the subjective or objective effects, and tolerance to the subjective intoxicating effects may develop more rapidly than tolerance to drug effects on psychomotor performance. This discordance is an especially dangerous combination for the safe use of drugs. Moreover, as noted above, drugs that produce feelings of euphoria may also impair judgment and cognitive function. Assuming that users are more aware of their subjective state of feeling 'high' than their level of impairment, this is important information to obtain, and provide directly to the users.

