Experimental protocol. Each subject will participate in three sessions (0, 7.5 mg and 15 mg THC) in counterbalanced order, separated by at least one week. The sessions will be conducted from 9 am to 1 pm. Upon arrival in the laboratory for each session subjects will provide urine samples to rule out recent use of opiates, stimulants, sedatives, cannabinoids, and breath samples for recent alcohol use and urine samples to test for pregnancy (women). Those who test positive for any drugs will be rescheduled and pregnant women will be dropped. Participants will then complete pre-drug mood questionnaires and their heart rate and blood pressure will be measured. They will then ingest a capsule containing 0, 7.5 or 15 mg Dronabinol with 100 ml water. One drug condition will be administered on each of the three days, in mixed order and under double-blind conditions. Subjects will complete the tasks 2 hours after ingesting the capsule, and heart rate and blood pressure, as well as mood questionnaires, will be measured at half hour intervals. At times when no experimental events are scheduled subjects will be free to relax, read or watch tv. Following the sessions subjects will be escorted to public transportation or provided with transportation home.

Drug. THC (Marinol® [dronabinol]; Solvay Pharmaceuticals) will be orally administered in doses of 7.5 mg and 15 mg, in opaque capsules with dextrose filler. Placebo capsules contain only dextrose. These doses of THC are known to produce performance impairments as well as subjective intoxication (Broyd et al, 2016; Hartman and Huestis, 2013).

Dependent measures.

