Data analysis and timeline. The primary outcome measures are i) actual performance on the app tasks; ii) actual performance on the desktop tasks. iii) predicted and perceived performance on each task, and iv) ratings of how "high" the subject feels. First we will examine the quality of the data to exclude grossly inappropriate responses (e.g., all minimum or all maximum values). Then we will determine whether there are orderly changes in task performance (i.e., improvement or decline) across the 3 sessions, and co-vary for session order if necessary. Then we will assess the effects of the drug on performance on each task and on the mood questionnaires using linear mixed models for repeated measures (Hedeker & Gibbons, 2006) with factors of drug condition and session time point, and random subject intercept and session effects. For drug condition, we will treat placebo as the reference cell and make comparisons of each drug level to placebo. We expect that the effects of THC on both subjective state and performance will peak two hours after drug ingestion. Finally, we will examine relationships across variables. We will examine the concordance in impairment using the desktop administered tasks and the tasks administered with hand-held devices. We will also examine the relationship between participants' estimates of the impairment and their actual impairment by calculating a ratio between the two (drug minus placebo for estimates: drug minus placebo for actual impairment). We expect that it will take one year to complete testing of 48 participants in the three sessions, and to conduct the analyses of the findings. Our goal is to have a fully functional and sensitive app ready to test in a non-laboratory, naturalistic setting.

Possible pitfalls. It is possible that the tasks, either app-based or computer based, will fail to detect THC-induced impairments. We will examine data from completed subjects as we go, and if we fail to see

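### The dose-placebo comparison for the repeatedly rated 'high' score has no stated time, its literal reading averages in the pre-drug value, and the sections contradict each other on when tasks are given

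*Combined protocol and SAP*

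**What the plan says.** Data analysis and timeline lists four primary outcomes: app-task performance, desktop-task performance, predicted and perceived performance, and ratings of feeling 'high'. Performance and mood questionnaires are analysed by linear mixed models "with factors of drug condition and session time point, and random subject intercept and session effects". For dose, "we will treat placebo as the reference cell and make comparisons of each drug level to placebo". The only time mentioned near that comparison is an expectation: "We expect that the effects of THC on both subjective state and performance will peak two hours after drug ingestion". Session order is adjusted for conditionally: "and co-vary for session order if necessary".

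Experimental protocol makes the first rating pre-drug: "Participants will then complete pre-drug mood questionnaires and their heart rate and blood pressure will be measured", and the capsule follows. On tasks it says: "Subjects will complete the tasks 2 hours after ingesting the capsule". Other sections give different times for tasks and ratings; they are set side by side in the working below.

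**The concern.** A model whose only listed fixed factors are dose and time within session gives one dose-placebo difference, averaged over every time analysed. For the 'high' rating that includes a value taken before the capsule, when no drug effect can exist. If an interaction is meant instead, the dose effect differs by time and the plan has to name the time it reports. The two readings give different estimates for a primary outcome, and the plan chooses neither.

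The same applies to app tasks, desktop tasks and self-estimates if the schedule that governs is one of those that repeat them within a session. If they are given once per session, they are not affected.

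The second matter is the schedule itself. The plan examines agreement between app and desktop impairment, and Possible pitfalls uses their relative sensitivity to decide whether the app tasks are kept or revised. If one set is given at 1.5 h and the other at 2 h, a difference in impairment could come from the time or from the device.

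**Working it through.** **1. Times given, section by section**

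| Section | App tasks | Desktop tasks | Ratings |
|---|---|---|---|
| Aim 1 | 2 h | 2 h; also brief performance tasks at the listed times | listed times |
| Approach | 2 h | laboratory performance measures half-hourly | half-hourly |
| Experimental protocol | 2 h (device not specified) | 2 h (device not specified) | pre-drug, then half-hourly |
| Selection of tasks | hourly | – | – |
| Computer-based tasks | – | 1.5 h | – |
| Self-report rating questionnaires | – | – | listed times; also before and after the tasks |

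The listed times are 0, 1.5, 1, 1.5, 2, 2.5 and 4 h: seven entries, six distinct times. Reading the first 1.5 as 0.5 is an assumption and gives seven times. Half-hourly over a 4-hour session gives nine (0, 0.5, ..., 4 h). Even with that assumption the list lacks 3 and 3.5 h, so a typing error alone does not reconcile the rating schedules.

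**2. What the main-effects contrast estimates**

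Let d(t) be the dose-placebo difference at time t, with T times. With balanced data the dose main effect is the mean of d(t) over the T times. Take d(0) = 0, because the 0 h value is pre-drug, and assume that no d(t) exceeds d(2), the plan's own expected peak. Then the contrast is at most (T − 1)/T of the 2 h effect:

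- list as printed, T = 6: 5/6 = 83%
- first 1.5 read as 0.5, T = 7: 6/7 = 86%
- half-hourly, T = 9: 8/9 = 89%

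**3. Size under assumed time profiles**

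The documents give no profile. Three assumed shapes, as shares of the 2 h effect at 0, 0.5, 1, 1.5, 2, 2.5 and 4 h, are:

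- middle: 0, 0.25, 0.5, 0.75, 1, 0.9, 0.5
- slow: 0, 0.1, 0.3, 0.7, 1, 0.95, 0.7
- fast: 0, 0.5, 0.8, 0.95, 1, 1, 0.8

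Six times (0.5 h left out): middle 3.65/6 = 61%, slow 3.65/6 = 61%, fast 4.55/6 = 76%.
Seven times: middle 3.90/7 = 56%, slow 3.75/7 = 54%, fast 5.05/7 = 72%.

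Dropping 0 h from the six-time average raises it to 3.65/5 = 73% (middle, slow) or 4.55/5 = 91% (fast). So the pre-drug value accounts for part of the gap, and averaging over rise and decline accounts for the rest.

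**4. Direction of the effect on power**

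Assume that within-subject dose-placebo differences have equal variance at each time and correlation ρ between times. The standardised effect of the average, relative to that of the 2 h contrast, is m / √((1 + (T − 1)ρ)/T), where m is the profile mean. With T = 6 and ρ = 0.5 (assumed), the denominator is √(3.5/6) = 0.764.

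- middle profile: 0.608/0.764 = 0.80, a loss
- effect flat after dosing: 0.833/0.764 = 1.09, a gain

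The sign depends on quantities that the documents do not give.

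**5. Variance for a 2 h contrast**

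A model with only random subject and session effects pools residual variance over doses and times. If placebo ratings sit near the floor and response to THC varies between people, the 2 h differences vary more than the pooled variance implies. Simulations on those assumptions gave 71–86% coverage for nominal 95% intervals from the pooled model, against about 95% for a paired 2 h comparison. Within that range, 4,000 trials per case with a between-person SD of 80% of the mean effect and the middle profile gave 77–85%. Naming the 2 h contrast is therefore not enough; its standard error must also allow for unequal variance.

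**The case against.** The best defence is that the plan already points to 2 h: it expects the peak there and places the tasks there. Nor does the text rule out a dose-by-time term; the opening section's purpose, "to determine the sensitivity and time course of the impairments in app-based task performance", favours one, although it speaks of app tasks and not of ratings. This stands as a reasonable guess at intent, but an expected peak is not a defined contrast. A session average would also be a valid quantity if the plan said that it was meant.

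Several stronger readings are tempting and are not supported:

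- *That the plan loses power.* Step 4 shows that averaging can lose or gain.
- *That the intoxication-performance question is answered with mismatched times.* Significance asks whether a user's "feelings of intoxication related to his or her impaired performance", but relationships are examined in a separate last step, and nothing says that a session-averaged 'high' effect feeds it. The mismatch is only a possibility.
- *That the conflicting rating schedules undermine a 2 h comparison.* Every version includes 2 h. Reading the ratings around the tasks as 2 h before and 2.5 h after is natural; a sentence confirming it is enough.
- *That app-task sensitivity, the main goal, is compromised.* If the 2 h schedule governs and app tasks are given once, their dose contrast is already unambiguous. Only the hourly wording in Selection of tasks brings them, and their self-estimates, into scope.
- *That all the desktop statements conflict.* Aim 1's computer tasks at 2 h and its brief performance tasks at repeated times may be different instruments. The 2 h against 1.5 h conflict remains.

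**Conclusion.** The point holds as an inexpensive improvement. It is not a flaw in the design. For the 'high' rating, and for task outcomes if a repeated schedule governs, the plan does not define its dose-placebo contrast. Read literally, the contrast includes a pre-drug value and is at most 83–89% of the 2 h effect, depending on the schedule. This bound assumes no effect at 0 h and none above the 2 h effect. Under the three assumed profiles the figure is 54–76%. These are differences in what is estimated; the documents do not support a claim about power in either direction.

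The contradictions over task times stand on the text alone. The conflict between 1.5 h and 2 h for desktop tasks matters most, because it leaves open whether the app-desktop comparison is made at one time or two.

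**What to change.** - **Schedule.** Reconcile Aim 1, Approach, Experimental protocol, Selection of tasks, Computer-based tasks and Self-report rating questionnaires on when app tasks, desktop tasks and ratings are given. State which rating counts as the 2 h value.
- **Repeated outcomes.** Use post-dose times only as responses. Fit dose, time, dose by time and session number. Make each dose minus placebo at 2 h the primary contrast, as the plan's own expected peak and task time, and the average over post-dose times secondary. Enter the session's 0 h value as a covariate where it varies; omit it where it does not.
- **Variance.** Do not pool over doses and times. Take the 2 h contrast from the 2 h data within subject (paired, adjusted for session number), or use a covariance that lets variance differ by dose and time, or use robust standard errors.
- **Once-per-session outcomes.** Fit dose and session number with a random subject intercept. With one value per session, a session-within-subject effect cannot be separated from residual error.
- **Session number.** Include it always, so that the model does not depend on a look at the data.

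The cost is analysis and schedule wording, two degrees of freedom for session number, one for the 0 h covariate where used, and those for the interaction. No extra subjects or visits are needed. The downside is that the primary contrast misses part of the effect if the peak is not at 2 h; the secondary post-dose average is there for that case.

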THC, the primary psychoactive ingredient of marijuana, is known to impair short-term memory, increase reaction time and impair attention. We will examine four tasks sensitive to the effects of THC using a simple app in a controlled setting (memory task, motor tapping task, reaction time and addition; Broyd et al, 2016; Desrosiers et al, 2015). The data obtained in the controlled setting will provide the basis for future testing in the naturalistic, field setting. Fifty-six healthy experienced but non-daily marijuana users will be recruited for a three-session laboratory study, in which they receive oral doses of THC (7.5 and 15 mg oral) and placebo under double blind conditions. They will be required to be THC-free at the beginning of the 4-hour sessions. During the sessions subjects will ingest the drugs and complete the app tasks two hours after ingestion, as well as standardized laboratory measures of performance and mood states at half hour intervals. Subjects will be asked to estimate their level of performance before and after each app task completion, without feedback on their actual performance. Cardiovascular measures (heart rate and blood pressure) will be obtained at regular intervals. The primary goal is to develop app tasks that are sensitive to the drug's effects and the drug dose on performance, as a model for future field testing.

We would like to expand on several methodological considerations and our responses to them.

1. Why use THC instead of marijuana? We have chosen to develop the app tasks with THC because the drug is readily available and because it has a known pharmacology, time course and dose effects. We recognize that we propose to use the app in a naturalistic setting where users will be using marijuana, and not THC, and where we have little control of the composition of the marijuana they will be using. However, to develop a task sensitive to the primary psychoactive ingredient of marijuana, we feel that oral THC is the drug with which we have the most control.
2. Why not obtain plasma samples of THC and its metabolites during each session, to link impairments to plasma levels of THC and its metabolites? This would be extremely valuable, and we have given careful consideration to the possibility of obtaining plasma samples. It would help to account for individual differences in absorption and metabolism, and to serve as a comparison to drug levels

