Participants. Healthy experienced but nondaily marijuana users (N=56 obtain, 48 completers; 24 men, 24 women 18-35 years) will be recruited with print and internet ads. Our ultimate target population in the future naturalistic phase of this project will be users who use occasionally but not daily, in order to obtain information about both drug-free and post-drug performance. We are not targeting daily users for this project because we wish to obtain baseline data from drug-free days as well as data from smoking days, to provide users with accurate feedback on their performance. Thus, only experienced, non-daily users will be recruited in this preliminary study. Participants will be screened according to Protocol 13681B, and accordingly must have at least a high school education, BMI 19-26, no current physical or psychiatric health problems determined by a physical examination, an electrocardiogram and an in-person psychiatric screening interview (SCID; First et al, 2015), no current medications, and no current substance use problems, based on the interview and a time-line followback. We will exclude women who are pregnant or planning to become pregnant. We will obtain detailed information about participants' drug use history, including their use of cannabis. Participants who meet criteria for Moderate or Severe Cannabis Dependence will be excluded (First et al, 2015), and subjects must agree to abstain from marijuana use to test negative for recent cannabis use at each session. For this protocol we will obtain information about habitual cannabis use (age at first use, period of heaviest use, past year use and current use over the past month), so that we may use level of use as a covariate in the analysis. We will also collect data on sex, age, height and weight to conduct exploratory analyses on these variables. Women will be tested any phase of the cycle except women who report serious premenstrual dysphoria will be tested during the follicular phase. We will record whether women are users of oral contraception and the phase of their menstrual cycle at each session.

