Sample Size and Power: We will test 48 subjects in this within-subject study. No previous studies have assessed the sensitivity of phone-based tasks to detect drug effects. We based the sample size on our own previous studies and other published reports using laboratory-based studies. Desrosiers et al (2015) detected effects of smoked marijuana (6.8% THC) on cognitive and psychomotor performance using a critical tracking task and a divided attention task using samples of 11 and 14 participants. We have found in a previous study (Ballard et al., 2013) that THC significantly impaired memory accuracy (relative to placebo) for positive and negative affective images, with large effect sizes in each case (partial eta squared = .20 and .13 respectively).

Orientation session. Subjects will first participate in a 1-hour orientation session to provide informed consent, agree to the study conditions described above, and practice the performance tasks. They will be instructed to refrain from any use of drugs or alcohol for 24 before the sessions and 6 hours after the sessions.

Participants will be advised that they must pass urine tests for recent drug use including marijuana, and to pass these tests they should abstain from use for one week if they are light users (1-2 times per week) and for two weeks if they are heavier users (e.g., daily). They will be instructed to abstain from smoking marijuana for the entire study. They will be told to have a normal night's sleep before the session, and a small breakfast before the sessions. Subjects will then practice the app tasks and the computer tasks to be used in the three sessions to minimize practice effects across the three study sessions.

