Selection of tasks: We have selected five app tasks from ResearchKit [<http://www.researchkit.org/docs/docs/ActiveTasks/ActiveTasks.html>] that are likely to be affected by marijuana (Broyd et al, 2016; Hartman and Huestis, 2013). These are spatial-span memory), finger tapping, reaction time, mental addition, and time perception/estimation. These tasks assess basic motor, psychological and cognitive function that THC and marijuana are known to affect (Broyd et al, 2016; Hartman and Huestis, 2013; Sewell et al. 2013). The tasks are relevant to everyday activities including safe operation of machines and accurate decision-making in a job setting. Note that the App to be used in the future naturalistic study will include additional features related to consent, demographic characteristics and data collection and management. However, for the present, laboratory-based study we will only use the App to administer the tasks and collect data on the hand-held device. We have selected four tasks from ResearchKit for initial testing, with the goal of selecting the three most sensitive tasks for the next stage of the project. The working software operates on a mobile device using Apple's ResearchKit framework. For the purpose of this laboratory-based preliminary study we will distribute the app to iOS devices we provide through the Apple "B2B" (business-to-business) distribution system. Reviewers wishing to examine the app should ask us for a redemption code that will give them access. Task performance and questionnaire data collected on the app will be transferred to an Access database on our main computer system.

The four tasks will be presented in mixed order at each hourly administration of the task. From these four tasks we propose to select the three tasks that are most sensitive to the effects of THC, and show the least change in learning across sessions.

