performance effects in the first 8 participants, we will try to increase the difficulty of the tasks. We will also consider including tasks other than the four we have proposed here, and we have the capacity to create new tasks using ResearchKit. Another possibility is that performance on the app tasks differs from performance on the computer based tasks. If the app tasks are more sensitive (to time or dose effects), we will continue to use these. If they are less sensitive we will again review the difficulty level of the app tasks, and attempt to harmonize the app tasks with the computer-based tasks.

Next steps. Once we have demonstrated that the app is sensitive to the effects of THC, we will be ready to test it in a non-laboratory setting. The ResearchKit apps are designed for use in real-world settings, and we expect to be able to proceed to the next phase with little further technical development. In the next phase, we will invite occasional marijuana users (N=20) to participate in a feasibility study, in which they agree to complete the tasks on 6 occasions when they have not used marijuana for at least 3 days to allow a reasonable time for the performance-impairing effects to return to normal and on 6 occasions when they have used the drug in the past 3 hours. (In the present project we will wait one week between sessions to allow full clearance of THC between sessions.) Subjects will provide informed consent, demographic information (age, sex, education), and information about their current habitual drug use. We will collect the data in a coded form, and compare the performance and performance evaluations to the findings from our laboratory study. Once we determine the sensitivity of the app to detect impairments when used outside the laboratory, we can proceed to offer the app on a larger scale to marijuana users who are interested in obtaining objective feedback on their level of impairment.

Literature cited

Broyd SJ, van Hell HH, Beale C, Yücel M, Solowij N. (2016) Acute and Chronic Effects of Cannabinoids on Human Cognition-A Systematic Review. *Biol Psychiatry*. 79(7):557-67.

Brumback, T, D Cao, A King (2007) Effects of alcohol on psychomotor performance and perceived impairment in heavy binge social drinkers. *Drug and Alcohol Dependence* 91:10–17

Chait, LD, JL Perry, Acute and residual effects of alcohol and marijuana, alone and in combination, on mood and performance. (1994) *Psychopharmacology* 15:340-9.

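### Sensitivity to dose is part of the primary goal, but the plan states no comparison of 15 mg with 7.5 mg, and the two placebo comparisons cannot stand in for one

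*Combined protocol and SAP*

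**What the plan says.** The Approach section of the combined protocol and SAP sets the target: "The primary goal is to develop app tasks that are sensitive to the drug's effects and the drug dose on performance". Drug effect and dose are named as two separate properties.

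Possible pitfalls returns to dose when weighing the app against the desktop versions: "If the app tasks are more sensitive (to time or dose effects), we will continue to use these".

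The design can address the question within person. Under Experimental protocol: "Each subject will participate in three sessions (0, 7.5 mg and 15 mg THC) in counterbalanced order".

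The analysis is in Data analysis and timeline. It is a linear mixed model "with factors of drug condition and session time point, and random subject intercept and session effects", and for drug condition "we will treat placebo as the reference cell and make comparisons of each drug level to placebo". No section names a contrast between the two active doses, a dose slope, or a rule for calling a task sensitive to dose. Sample Size and Power discusses effects of THC against placebo or of smoked marijuana, and gives no figure for a between-dose difference.

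**The concern.** A comparison of 7.5 mg with placebo and one of 15 mg with placebo each ask whether that dose does anything. Neither asks whether the higher dose does more. A task impaired equally by both doses and a task whose impairment grows with dose can give the same two significant results, yet only the second meets the dose part of the goal. The difference matters because the eventual app is meant to tell users how impaired they are.

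If dose sensitivity is nevertheless to be reported, the obvious material at hand is the pair of p-values, with 15 mg significant and 7.5 mg not being read as a dose effect. That reading has no controlled error rate. At stake are the dose half of the primary goal and the dose element of the app-versus-computer decision.

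**Working it through.** **Inputs**
- Completers: 48, from Participants ("N=56 obtain, 48 completers; 24 men, 24 women 18-35 years") and Sample Size and Power.
- Effect sizes: partial eta squared .20 and .13, quoted in Sample Size and Power for THC against placebo on memory accuracy for emotional images. The plan does not give the THC dose behind them.
- Significance level and power: not stated. Assumed here: two-sided 5%, with 80% power as the benchmark.
- Simulation: 100,000 three-period crossovers per setting, complete data, equal variances and correlations, SD of every paired difference set to 1.

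**The plan's own figure.** The 48 has no level, power or target contrast attached, so it cannot be reproduced. A paired t test at two-sided 5% needs 34 completers (80% power) or 44 (90%) for eta squared .20, and 55 or 73 for .13. None of these is 48.

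**Step 1: paired standardised effect.** If each eta squared is a one-degree-of-freedom contrast with error df close to n, dz = √(η²/(1 − η²)).
- .20: √(.20/.80) = 0.50
- .13: √(.13/.87) = 0.387

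**Step 2: power of a placebo comparison.** Noncentral t, 47 df, noncentrality dz × √48.
- 0.50 × 6.928 = 3.46, power 92%
- 0.387 × 6.928 = 2.68, power 75%

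The planned comparisons are therefore reasonable for detecting a THC effect of this size.

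**Step 3: what they show when dose makes no difference.** Same true effect at 7.5 mg and 15 mg:

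| Result | dz 0.387 | dz 0.50 |
|---|---|---|
| Both doses significant v placebo | 61.2% | 86.9% |
| 15 mg significant, 7.5 mg not | 13.3% | 5.5% |
| Direct 15 v 7.5 mg contrast significant, either direction | 5.1% | 5.0% |
| Direct contrast wrongly favouring 15 mg (half the row above) | about 2.5% | about 2.5% |

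The 15-mg-only pattern has an error rate that moves with the unknown effect size (about 17% at dz 0.30). The direct contrast holds its level.

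**Step 4: would a linear trend do?** Doses 0, 7.5 and 15 have mean 7.5, so the centred doses are −7.5, 0 and 7.5, with sum of squares 112.5. With complete data the slope is 7.5 × (y15 − y0)/112.5 = (y15 − y0)/15. The 7.5 mg result drops out, and slope × 15 is the 15 mg versus placebo difference. With no dose difference, that contrast is still significant in 75% (dz 0.387) or 92% (dz 0.50) of trials.

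**Step 5: power of the direct contrast at n = 48.**
- Detectable dz at 80% power: 0.41. Normal approximation: (1.960 + 0.842)/√48 = 0.404.
- If the quoted effect applies to 15 mg and is linear in dose, the between-dose effect is half of it. For 0.50/2 = 0.25, power is 40% (128 completers for 80%). For 0.387/2 = 0.193, power is 26% (213 completers).
- If the gap is one third to two thirds of the 15 mg effect, power is 20% to 62% (η² .20) or 14% to 42% (η² .13).

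**The case against.** The strongest reply is that this is a self-described proof-of-concept study, that the three-level drug factor already yields both dose estimates, and that their difference can be taken from the fitted model at any time. That is true, and it is why the fix is cheap. But a contrast that could be taken is not a planned one, and an overall three-level test would not isolate dose.

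A second reply is that the direct contrast is weak at 48 completers. This also stands: under linearity a truly graded task would more often than not fail to reach significance. The 15-mg-only pattern does arise more often under a linear effect (54% at dz 0.50, 51% at 0.387). But it also arises in 5.5% or 13.3% of trials with no dose difference, so the gain comes at an uncontrolled error rate. Low power is a reason to report an estimate with its interval, not to infer dose sensitivity from the placebo tests.

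Three stronger readings are tempting, and the documents do not support them.
- A reader might infer that the choice of three tasks is compromised. Selection of tasks says the aim is to "select the three tasks that are most sensitive to the effects of THC, and show the least change in learning across sessions". Dose is not a criterion there, and placebo contrasts can address the THC part.
- A reader might infer that the plan intends to read dose from the pattern of p-values. It does not say so; it leaves dose sensitivity undefined.
- A reader might count every trial with exactly one significant dose as misleading: 2 × 13.3% = 27%, or 2 × 5.5% = 11%. Half of those have only 7.5 mg significant, which nobody would take as impairment rising with dose.

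**Conclusion.** The point holds. A stated part of the primary goal, also invoked in the app-versus-computer decision, has no matching analysis, and the comparisons that are planned cannot supply one. With equal true effects, both placebo tests are significant in about 61% to 87% of trials, and the misleading 15-mg-only pattern appears in about 13% to 5.5%, against 2.5% for the direct contrast. At dz 0.50 that excess is only about 3 percentage points, so the main defect is the missing estimate rather than a large false-positive rate.

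These figures assume two-sided 5% tests, complete data, equal variances and correlations, and effects borrowed from a different memory outcome. That no between-dose contrast is planned depends on none of these assumptions. The planned tests of each dose against placebo remain sound for their own question. The change should be made before results are examined.

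**What to change.** In Data analysis and timeline, add the within-subject 15 mg versus 7.5 mg contrast from the same mixed model, with its 95% confidence interval, for each app task and each desktop task, naming the assessment time it refers to. State that sensitivity to dose, in the primary goal and in Possible pitfalls, is judged on that estimate and interval, and that the placebo contrasts are used for sensitivity to THC. Do not offer a linear trend over 0, 7.5 and 15 mg as an alternative.

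The cost is one more contrast per task from a model already planned, with no new data or visits. The real drawback is precision. With 48 completers the 95% interval extends about 2.012/√48 = 0.29 SD of the paired difference either side of the estimate, and 80% power needs a between-dose dz of about 0.41. The plan should say so, present the contrast as estimation, and accept that some tasks may be reported as sensitive to THC with dose sensitivity unresolved.
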